3.3 Proposed activities and outcome

This individually randomised study will compare the two artesunate formulations: the speed and convenience of preparation and use, the costs of drug administration, and basic pharmacodynamic measures as well as adverse events. A mixed method social science study will explore the opinion of healthcare workers and policymakers regarding the use of the new compared to the old artesunate formulation. To ensure policymakers and stakeholders are familiar with the topic for the SSIs, i.e. 1-step artesunate injection versus 2-step artesunate injection (conventional treatment), a brief video documenting how the artesunate injection is prepared and administered (1-step versus 2-step artesunate injection) will be recorded. The video will only serve to familiarize the topic for

SSIs with the policymakers.

The main activity is an objective assessment of the convenience to use the artesunate formulations, as well as an *in vivo* clinical and parasitological assessment in 200 participants with severe falciparum malaria at two sites: 1 in DRC and 1 in Tanzania. The subjects will be randomized between the 1-step parenteral AS and conventional 2-step parenteral AS (currently standard of care at both sites).

The secondary activity proposed is a cost analysis of 1-step AS vs conventional 2-step parenteral AS.

The third activity is a feasibility and acceptability survey using mixed methods social science study with health workers and policymakers to explore their experience and opinions related to using 1-step AS compared to the old formulation.

All research-related activities, from study design, planning, implementation through to analysis and writing of reports will be performed jointly with local counterparts. Both on-the-job training and formal training will be provided when needed, including Good Clinical Practice (GCP) skills. The close interaction between WHO and its regional offices will ensure that new knowledge is disseminated efficiently and effectively. The trial will be overseen by a Data and Safety Monitoring Board (DSMB).

4. OBJECTIVES

4.1. Co-primary Objectives

Assessment of:

- (1) Convenience and rapidness of administration of 1-step vs. conventional 2-step parenteral artesunate formulations
and
- (2) Costs of administration of 1-step vs. conventional 2-step parenteral artesunate formulations

4.2. Secondary Objective

- (1) To assess the acceptability, policy and implementation perspectives, and health care worker satisfaction regarding the use of 1-step formulation of parenteral artesunate.

4.3. Exploratory Objectives

- (1) To assess and compare *P. falciparum* parasite clearance rates of 1-step vs. conventional 2-step parenteral artesunate formulations.
- (2) To assess and compare time from intravenous treatment to follow up treatment with oral drugs with 1-step vs. conventional 2-step parenteral artesunate formulations.
- (3) To assess and compare disease outcome parameters between 1-step vs. conventional 2-step parenteral artesunate formulations.
- (4) To assess and compare adverse events between 1-step vs. conventional 2-step parenteral artesunate formulations.

5. TRIAL DESIGN

5.1 Study sites

The study will take place at 1 site in the DRC and 1 site in Tanzania.

- Magunga District Hospital, National Institute for Medical Research (NIMR) Korogwe Research Laboratory, Korogwe, Tanga Region, Tanzania.
- The Kinshasa Mahidol Oxford Research Unit (KIMORU), Kinshasa, DRC.

Malaria transmission at both sites is endemic and both sites estimate numbers of pediatric patients attending with suspected severe malaria is greatly in excess of the number of patients necessary for screening and enrollment into the present study.

5.2 Summary of trial design

Part 1

A comparison of 1-step parenteral artesunate vs. conventional 2-step parenteral artesunate in patients with severe malaria to assess the feasibility of administration, parasite and fever clearance times of 1-step parenteral AS to conventional AS in 2 countries. Patients with severe malaria will be enrolled and randomly allocated to treatment with conventional injectable artesunate or 1-step injectable artesunate. A Time and Motion study will record the time to prepare the artesunate solution for injection and administer treatment, number of actions performed to prepare treatment, and consumables used. Clinical, parasitological, and laboratory assessments will be recorded while patients are admitted in hospital and then weekly up to day 28 to assess recovery and determine final status.

Part 2

A mixed method social science study that entails SSIs and survey with study staff (involved in part 1), health workers (who treat severe malaria) and policymakers and stakeholders (who are involved in devising national malaria policy and its implementation), to assess the acceptability, feasibility, pros and cons, costs, and logistics and training implications of 1-step AS vs conventional AS. For both sites, SSIs will be conducted with minimum of a total of 40 respondents consisting of study staff, health staff and policy makers and stakeholders. The ultimate sample for SSI will be dependent on the data saturation [20]. For survey/questionnaire, a maximum number of relevant participants (study staff and health care staff) will be attempted to be recruited from two sites. A minimum of 150 study staff and health care staff will be recruited in the survey.

Part 3

A cost analysis of 1-step parenteral AS using data from Part 1 & Part 2. This will assess health facility-level costs, and also health system costs to encompass all costs of a potential change from conventional to 1-step artesunate, including re-training, materials, drug replacement.²⁰

5.3 Study duration

The recruitment phase of the study is expected to last 12 months once a site starts to recruit. The sites intend to start recruiting patients during Q4 2021. Training will precede study execution by up to 1 month. The mixed method social science study and costing analysis will take place during Q1 and Q2 2022 and run in parallel with the main study. SSIs with policy stakeholders will take place in Q2 and Q3 2022 to allow findings from the study and experiences and opinions of health workers to be discussed. Data management and analysis, and report writing and submit for publication in peer-reviewed medical journal are expected to take about 6 months per site. Therefore, the total time to complete the study will be about 18 months.

5.4 Primary and secondary endpoints

5.4.1. Primary Endpoint

- (1) Time to administration of treatment comparing 1-step vs. conventional 2-step parenteral artesunate formulations (by time-and-motion methods).
and
- (2) Costs of administration of 1-step vs. conventional 2-step parenteral artesunate formulations at health facility, and at health system level.

5.4.2. Secondary Endpoints

- (1) A mixed method social science study will assess feasibility, practicability, and satisfaction of 1-step for-mulation of parenteral artesunate. (To include study staff, health staff, and policy-makers and stakeholders)

5.4.3. Exploratory endpoints

- (1) Parasite clearance half-life and other parasite clearance parameters (PC50, PC90, 12-hour parasite reduction ratio) compared between 1-step vs. conventional 2-step parenteral artesunate formulations.
- (2) Time from start parenteral treatment to follow up treatment with an oral ACT (recovery to per os treatment) of 1-step vs. conventional 2-step parenteral artesunate formulations.
- (3) Fever clearance time (i.e. the time taken for the tympanic temperature to fall below 37.5°C and remain there for at least 24 hours) of 1-step vs. conventional 2-step parenteral artesunate formulations.
- (4) Incidence of adverse events and serious adverse events by study arms within the first 28 days.

5.5 Trial Participants

5.5.1. Overall Description of Trial Participants

This will be an open-label, randomised trial. All study patients must meet the applicable inclusion and exclusion criteria. The treating physician will decide whether the patient is severely ill and eligible for inclusion.

5.5.2. Inclusion criteria

Part 1:

- Male and female children aged >3months and <16 years.
- Clinical diagnosis of severe *P. falciparum* malaria; or parasitological confirmed *P. falciparum* hyperparasitaemia >350,000/ uL.
- Positive malaria test result, by rapid diagnostic test RDT.
- Weight of 5 kg or greater.
- Written informed consent by the parent or guardian.

Part 2:

Study staff and health staff

- Study staff who prepare and administer Artesunate injection to patients in the study or health staff who have not administer the Artesunate injection to patients in the study by themselves

but are either aware of malaria treatment, Artesunate injection, or have observed the treatment provided to severe malaria patients.

- Written informed consent by the study staff and health staff

Study staff for a short video-record

- Study staff who would like to participate in the video record of a procedure to show how 1-step and 2-step Artesunate injections are prepared and administered.
- Written informed consent by the study staff

Policymakers and stakeholders

- Those who are working in the National Malaria Control Program (NMCP) or relevant organizations (WHO, INGOs/NGOs) within the country.
- Written informed consent by the potential participant

5.5.3. Exclusion criteria

Part 1:

- Participation in other intervention studies
- Known allergy to artemisinin derivatives.
- Known history of parenteral treatment for severe malaria for the current episode of illness before admission. Treatment before admission with an oral antimalarial drug (used for the treatment of uncomplicated malaria) or a single dose of pre-referral rectal artesunate are not exclusion criteria.

Part 2:

Study staff and health staff; Policymakers and stakeholders; Study staff and health staff for a short video-record

- Unwilling to participate in the study
- Unable to communicate

6. PROCEDURES

Part 1

A trial nurse will receive all children who could have severe malaria and are potentially eligible to participate in the study and call the attending physician. The diagnosis of *falciparum* malaria will be made by a PfHRP2-based rapid malaria test. If the test is positive, and there is a clinical judgement that the patient has severe disease (according to a check list provided in the Case Report Forms [CRFs]), the patient can be enrolled, provided written informed consent has been obtained and all eligibility confirmed. The screening sequence will differ for patients with hyperparasitaemia only with no symptoms of severe malaria, as their eligibility will be determined when microscopy results are available, if performed.

Once the patient is enrolled, the randomisation deciding the drug allocation will be carried out. This is done in the following way: The next in a series of numerically sequenced envelopes is opened. The envelope will contain the unique participant number. From the moment the envelope is opened the patient is considered in the study whether or not the protocol is followed correctly thereafter. The envelope contains a slip of paper with a treatment box code number. The treatment box with this code number is then opened.

With the help of the study nurse, the attending physician will take the patient's history, and do a physical exam, where the list in the Case Report Forms (CRFs) serves as a guideline. Parameters include basic demographic parameters, questions regarding the previous history and current history, vital signs, coma score, and others. Patient monitoring during admission: to assure the best possible treatment of each study patient the following variables will be monitored based on WHO guidelines²¹

A detailed monitoring sheet will outline the planned observations and their frequency. In case of abnormal findings staff will be trained to repeat the test and to inform the key decision makers regarding the need to change the management of the patient. To help the treating physician, a practical guideline on the treatment of severe malaria (appendix 4) will be provided to all involved physicians.

When the patient is well enough to take and retain oral medication the attending clinician will be free to prescribe first line antimalarial therapy, according to national guidelines ensuring that a complete course of treatment is provided. In the case of Tanzania and DRC this will be an ACT (to be artemether-lumefantrine if available and not contraindicated, otherwise or other ACT and will be prescribed according to weight. The patient will be encouraged to stay on the ward until the complete course of ACT is taken. If the patient is discharged from hospital before the full course of ACT is administered, the remaining doses will be given to the attending caregiver with clear instructions.

A time and motion design will be employed to record ease of administration of 1-step vs conventional artesunate. Each nurse administering the IV artesunate will be paired with an additional study team member acting as an observer. The observer starts the stopwatch when the nurse breaks the seal of the IV artesunate package and stops the stopwatch when preparation of the artesunate solution for injection is completed. The time, in minutes and seconds is recorded by the observer in the CRF. This methodological approach is considered appropriate for short tasks and provides detailed field data, and typically requires a 1:1 observer to subject ratio.²²

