6.3. Randomisation and blinding

Patients will be randomised to treatment with either conventional 2-step parenteral artesunate (1) or 1-step parenteral artesunate (2). Patients who fulfil all the inclusion criteria and have none of the exclusion criteria will be randomised 1:1 to one of the two treatment arms according to a randomisation schedule. Randomisation will be in blocks of 8-12. Allocation will be done by drawing the next sequential numbered opaque envelope, which contains the study number and treatment allocation.

The patients will be assigned a study arm through a computer-generated randomisation schedule by the study statistician in MORU. Individual, sealed and sequentially numbered envelopes will be provided for each trial site with one envelope per patient, indicating the treatment allocation. This is an open-label study so the blinding of investigators and patients is not applicable. However, the randomisation procedure allows for adequate drug allocation concealment before envelopes are

opened. All laboratory investigations will be performed without knowledge of the treatment allocation.

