7.2 Compliance with Study Drugs

Parenteral study drugs will be administered by study medical staff (either a doctor or nurse). The first dose of ACT will be administered by DOTs and if the patient vomits ACT, and is re-dosed; this will be recorded in the CRF. If vomiting within 1 hour occurs again after retreatment, no repeat dosing is allowed. In this case the patient will be treated at the discretion of the Investigator. The patient may be discharged if recovered in the opinion of the study physician even if the full 3-day course of ACT is not complete. All drug doses will be recorded in the CRF.

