9. STATISTICAL CONSIDERATIONS

9.1. Sample size justification

Part 1:

Sample size calculations for non-inferiority study is based on dissolution test data from Guilin Pharmaceutical Co. Ltd. ("Study report on the solubility of artesunate for injection (60mg), Doc. RR-QC-ZSYQHHZ (60mg)RJX-2021 30th April 2021).²³ This is supported by unpublished in-house experience (from a bioequivalence study in healthy volunteers, personal communication, [name], Mahidol University) that the conventional formulation takes about 4 minutes with a standard deviation of 2 minutes to administer injectable artesunate. Our non-inferiority margin is 1 minute of drug re-constitution for the new simpler artesunate formulation i.e. if participants in the 1-step artesunate formulation will have a mean of the time of 5 minutes or less of drug re-constitution, with a standard deviation of 2 minutes, then the new formulation will be considered to be non-inferior to the old formulation. With this non-inferiority margin, detecting non-inferiority with 90% power and with a one sided alpha of 0.025, we will need to recruit 85 participants in the new formulation and 85 in the old formulation arm giving a total of 170 participants. In order to compensate for a 15% loss to follow-up or withdrawal, we will need 100 participants in each arm giving a total of 200 participants in the two arms combined. These calculations were performed in Stata 16 (StataCorp LLC Software).

The sample size calculation dovetails with pragmatic needs for the other study activities the 200 participants provides sufficient variability of participant characteristics to allow staff to gain experience of using 1-step artesunate and be able to provide an informed opinion of its pros and cons. Recruitment of 100 patients per site is feasible over 12 months based on the expected numbers of cases of severe malaria ([name] and [name], personal communication April 2021). The sample size calculation is based only on the time-to-treatment of participants and not on the costing analysis.

Part 2:

Number of respondents (sample size) for this study will be based on the principles of 'data saturation', that is data are collected until no new data/themes emerge from further interviews. A minimum of 40 respondents in total will be recruited for the SSIs, and at least 150 health workers will be interviewed with the survey questionnaire.

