2. GENERAL ANALYSIS APPROACH

The principle of intention to treat (ITT) will be the main strategy of analysis for the primary outcome. These analyses will be conducted on all patients assigned to the treatment groups as randomised. Any patients subsequently found not to be eligible during the trial or that did not receive a full course of study drug will be included in these analyses. Per Protocol (PP) analysis will be conducted to examine robustness of ITT results. This will be a form of sensitivity analysis to the intention to treatment analysis principle. In the PP analyses, all patients wrongly included in the study based on the inclusion/exclusion criteria will be excluded from analyses.

The cost analysis of 1-step parenteral AS will assess health facility-level costs, and health system costs to encompass all costs of a potential change from conventional to 1-step artesunate, including re-training, materials, drug replacement. Unit costs will be assigned to healthcare worker time spent on managing patients with severe malaria (derived from the time and motion surveys). Micro costing will be carried out in each of the sites to estimate the costs of equipment and consumables associated with provision of artesunate with each of the formulations. The resulting labour and consumable mean costs will be compared in patients treated with 1-step vs conventional artesunate formulation.

Time from opening box to completed preparation of syringe will be summarised using means and standard deviation for each each arm. Difference in means and the correponding 95% confidence intervals will be reported. We will provide overall comparisons by arm as well as for each site separately. The comparisons will be done for baseline times ans well as for all recorded times. Total cost of consumables in US dollars will be summarised in a similar way. A Student's independent t-test will be used for comparison of means between groups. The Central Limit Theorem justifies the use of the Student's t-test even if the times/costs may not be normally distributed because of the large sample size. However, if the data will be highly skewed, non-parametric tests such as Manny-Whitney (Wilcoxon) U test will be considered. Statistical significance will be declared at 5% significance level.

Data analysis will be performed using Stata 17 or higher, StataCorp, 4905 Lakeway Drive College Station, Texas 77845 USA

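### Nothing fixes who prepares the injection before the arm can be seen, and the analysis ignores the preparer: an unguarded bias risk on the preparation-time co-primary endpoint

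*Protocol*

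**What the plan says.** Protocol Section 6 gives the order of events for Part 1. The next envelope is opened, and then "The treatment box with this code number is then opened". Under Section 6 the envelope holds a participant number and a box code. Section 6.3 says that it contains the treatment allocation itself. Section 6.3 also says "This is an open-label study so the blinding of investigators and patients is not applicable".

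The timed task is described in Section 6: "Each nurse administering the IV artesunate will be paired with an additional study team member acting as an observer". The observer runs the stopwatch from the moment the nurse breaks the package seal until the solution is ready. No rule says which nurse this is, or that the nurse is named before allocation. Randomisation uses blocks of 8-12 with envelopes supplied per site; operators and shifts play no part in it.

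The items that the observer records are the time (Section 6) and the vials and consumables used (the Part 3 costing text before Section 6.7). The preparer's identity is in neither list.

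SAP Section 2 states that an "independent t-test will be used for comparison of means between groups". The comparison is made overall and by site, for baseline times and for all recorded times. Neither that section nor SAP Table 2 has a preparer term.

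**The concern.** The nurse's hands produce the outcome. Randomising children balances the children's characteristics, but it cannot balance a choice made after the arm is visible. The protocol's own background calls the 2-step procedure error-prone and sometimes difficult to dissolve, and Section 9.1 expects staff to gain experience with the new product. Either could steer a particular nurse towards a particular box, and the resulting bias could favour either arm.

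Two results are exposed. One is the mean difference in preparation time, judged against a 1-minute margin. The other is the labour part of the cost co-primary, because staff time is priced from the same time-and-motion data (Protocol Section 9.2.1). Even if non-inferiority is easily met, a biased figure for minutes saved passes into the cost comparison. If the preparer is never recorded, no later analysis can detect or repair an imbalance.

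**Working it through.** **Inputs from the documents (Protocol 9.1, repeated in SAP 2.2.1).** The design is stated as "Sample size calculations for non-inferiority study is based on dissolution test data from Guilin Pharmaceutical Co. Ltd". The control figures are that "the conventional formulation takes about 4 minutes with a standard deviation of 2 minutes to administer injectable artesunate". The margin is "Our non-inferiority margin is 1 minute of drug re-constitution for the new simpler artesunate formulation". Power is 90%, one-sided alpha 0.025, with 85 per arm, or 100 per arm after 15% loss.

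**Step 1: reproduce the plan's figure.** n per arm = 2 × [SD × (1.96 + 1.2816) / margin]² = 2 × (2 × 3.2416 / 1)² = 84.06, rounded up to 85. Then 85 / (1 − 0.15) = 100. Power at 85 per arm is 0.903. The stated size is correct for independent observations. At 100 per arm, SE = 2 × √(2/100) = 0.283 minutes.

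**Step 2: assumptions not in the documents.** There are 12 preparers. The share of total variance lying between preparers (ICC) is 0.1, 0.3 or 0.5. Faster staff make 60% of preparations in one arm and 40% in the other, a 0.20 difference in share. The documents give none of these figures, so a range is shown.

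**Step 3: size of the shift.** Between-preparer SD = 2 × √ICC. For 12 normally distributed preparers, the faster and slower halves differ on average by about 1.50 between-preparer SDs. Shift = 0.20 × 1.50 × 2 × √ICC. The chance of wrongly declaring non-inferiority when the true difference is 1 minute, with the tilt favouring 1-step, is Φ(shift/0.283 − 1.96). Power at no true difference, with the tilt the other way, is Φ((1 − shift)/0.283 − 1.96).

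| ICC | Preparer SD (min) | Gap between halves (min) | Shift at 60/40 (min) | False non-inferiority (nominal 0.025) | Power, adverse tilt (0.94 without tilt) |
|---|---|---|---|---|---|
| 0.1 | 0.63 | 0.95 | 0.19 | 0.10 | 0.82 |
| 0.3 | 1.10 | 1.64 | 0.33 | 0.21 | 0.66 |
| 0.5 | 1.41 | 2.12 | 0.42 | 0.32 | 0.53 |

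At these shifts a nominal 95% interval covers the true difference about 90%, 79% and 68% of the time. Simulation gives nearly the same values.

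**Step 4: neutral choice of preparer.** I simulated 100 per arm and 12 preparers, with choice unrelated to arm and one effect common to all preparers.

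| ICC | True SE of unadjusted difference | Mean t-test SE | 95% coverage | SE after preparer adjustment |
|---|---|---|---|---|
| 0.1 | 0.28 | 0.28 | 0.94 | about 0.27 |
| 0.3 | 0.28 | 0.28 | 0.95 | 0.24 |
| 0.5 | 0.28 | 0.28 | 0.95 | 0.21 |

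The adjusted SE is close to 0.283 × √(1 − ICC), which gives 0.268, 0.237 and 0.200, plus a small loss from estimating the preparer effects. In this case the t-test interval is sound, and adjustment only narrows it.

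**The case against.** The strongest reply is that no passage says preparers are chosen by arm. A trial nurse receives the child before enrolment, and the team aims to treat within one hour of presentation (Protocol 6.1), which leaves limited room to swap staff. If the envelope shows only a box code, as Section 6 says, the nurse and observer may already be in place when the product is seen. This narrows the risk but does not close it. Section 6.3 says the envelope contains the allocation, and no rule ties the receiving nurse to the preparation.

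A reader might infer that doctors also make timed preparations, because Section 7.2 says "Parenteral study drugs will be administered by study medical staff (either a doctor or nurse" may do so. That sentence concerns administration. Section 6 has a nurse do the timed task, so the documents do not support this inference.

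A reader might also infer that the t-test interval is too narrow simply because a limited pool of staff produces all the timings. Step 4 shows otherwise for first-dose times when the choice is neutral and the effect is common. The interval would be too narrow if operators were unevenly spread over the arms, or if the 1-step effect varied materially between preparers and the target were nurses in general. The documents state neither.

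The magnitudes rest on assumptions, and an ICC of 0.5 is high. It implies a gap of about 2.1 minutes between faster and slower staff on a task averaging 4 minutes. Shaking of several minutes is described for both products, and the vial count depends on the child's weight. For that reason the low end (ICC 0.1, 0.19 minutes) is shown alongside. Lastly, the CRF and SOPs were not available and may already capture the preparer. The SAP would still make no use of it.

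**Conclusion.** The concern stands as an unguarded risk on a co-primary endpoint. On the text, the preparer is not fixed before the arm can be seen, is not listed for recording, and is not in the analysis. The documents do not show that preparation time is in fact confounded with operator speed, and that stronger claim should not be made.

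With SD 2 minutes, 12 preparers and 10-50% of variance between preparers, a 60/40 tilt of faster staff would use up about 0.2-0.4 minutes of the 1-minute margin and would also distort the labour-cost difference. Without a tilt, and with a common effect, the first-dose t-test is about right. The gain from adjustment is then precision: the SE falls from 0.28 to between about 0.27 and 0.21. The sample size needs no change. This is a cheap improvement in method, not a fatal flaw.

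**What to change.** **Protocol Section 6.** Enter the first-dose preparer on the CRF before the envelope is opened, and record a preparer code for every timed preparation. At later doses the arm is already known, so the code is the only safeguard there.

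**SAP Section 2.** Estimate the first-dose mean difference and its 95% confidence interval from a linear model with arm, site and preparer (within site). Keep the t-test as a supporting analysis. A preparer-by-arm random effect is optional and exploratory, because it may be unstable with few preparers.

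**Cost.** One CRF field, unless it already exists, a few sentences of protocol and SAP text, and slightly less flexibility on shift. No dose or clinical rule is affected.
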